11.9.4 Disposition of Subjects

The numbers of subjects who were enrolled will be provided. A list of discontinued patients, protocol deviations, and patients excluded from the efficacy analysis will be provided as well.

11.9.5 Analysis of Primary Endpoint

A 2x2 table of the results of all subjects who had valid results on both AEYE-DS and the Reader Center comparing the positive/negative results obtained from the AEYE-DS versus the reference values will be presented.

The primary efficacy analysis will present the estimation of sensitivity and specificity of the of the AEYE-DS device to detect mtmDR on digital funduscopy images (acquired by the TopCon NW400 funduscopy device based on one macula centered image obtained per eye) together with their lower limit of their respective one-sided exact 97.5% confidence intervals. If the lower limits of the one-sided 97.5% confidence intervals of the sensitivity and specificity are greater than or equal to 82% and 87% respectively the null-hypotheses will be rejected. If both null hypotheses are rejected in favor of the alternative hypotheses the study will be deemed successful, and the performance goals met.

The positive and negative predictive values (PPV and NPV respectively) of the diagnosis together with their respective exact 95% confidence intervals will be presented as well.

Analyses will be performed on both ground truth modalities, fundus-only and multi-modality (using funduscopy and OCT).

The percent of participants requiring pharmacologic dilation and not requiring dilation to obtain an AEYE-DS disease level output will be calculated.

Sensitivity and specificity, analyses will be carried out on the combined cohorts. [Redacted content]

[REDACTED]

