	
on digital funduscopy images in patients with known diabetes undergoing screening for diabetic retinopathy.
 
 ○ To assess the specificity of the AEYE-DS software device for the detection of more than mild diabetic retinopathy (mtmDR) on digital funduscopy images in patients with known diabetes undergoing screening for diabetic retinopathy. 
Digital funduscopy images will be acquired by the TopCon NW400 funduscopy device based on 2 images obtained per eye, one macula centered and one optic-disc centered.

Secondary Objectives
	
 ● Secondary Objectives: 
 ○ To assess the imageability of AEYE-DS, defined as the percentage of participants with a disease level output (mtmDR+ or mtmDR-) from the AEYE-DS device. ○ To assess the Usability of the AEYE-DS device, including User Manual comprehension and subsequent usability of the device in the hands of potential users (i.e., primary care clinicians). ○ To assess the sensitivity and specificity of the AEYE-DS software device for the detection of more than mild diabetic retinopathy (mtmDR) on digital funduscopy images obtained from a handheld funduscopy device, in patients with known diabetes undergoing screening for diabetic retinopathy. Digital funduscopy images will be acquired using the Optomed Aurora handheld funduscopy device based on one macula-centered image obtained per eye.

Study Hypothesis
	
In this study, we will test the following pairs of hypotheses on the primary endpoint, as well as on the powered secondary endpoint:
 
 ● H0: Se \leq 82%, H1: Se > 82% ● H0: Sp \leq 87% H1: Sp > 87% 
Where Se and Sp are the sensitivity and specificity of the mtmDR classification of the AEYE-DS software device.

Sample Size
	
At least 66 positive and 265 negative subjects are required to meet the primary and powered secondary endpoints.
 
The study will follow a sample size adaptive design with one interim analysis planned to allow for sample size increase up to at most 774 subjects, or completion per original sample size.
 
██
 
██
 
██

	
[REDACTED]

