5 RATIONALE FOR STUDY

Based on a recent global report [WHO, 2014], there are over 422 million people worldwide with diabetes, and over 35% have signs of DR, a third of them with vision threatening DR. With the prevalence of diabetes expected to increase 50% over the next 10 years, screening rates, detection, and treatment must be addressed in order to prevent a significant increase in unnecessary blindness across the United States. Early detection of retinopathy through periodic screening is an important part of managing care for people with diabetes, yet screening rates are low, with only 50-60% of diabetic patients properly evaluated. An automated DR screening device would allow for immediate screening results at the point of care and standardization of results.

[REDACTED]

[REDACTED] The current proposed study will validate the sensitivity and specificity of the AEYE-DS output by a novice operator compared to the reference standard, diagnostic determination by an independent, blinded panel of expert ophthalmologist at the reading center.

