7 SELECTION OF STUDY POPULATION

The goal of the selection criteria is to identify adult patients who have undergone digital funduscopy imaging with clinical evidence of diabetes and are screened to rule out diabetic retinopathy. The study population will consist of adult patients (at least 22 years of age) with previously diagnosed diabetes, who are participating in a routine retinal screening test for diabetic retinopathy (DR) in primary care clinics, and have digital funduscopy images of sufficient quality from a specific funduscopy camera, i.e., the Topcon Model NW400. The patients referred to the screening program must be without prior diagnoses of DR. "Diabetic" patients are defined in the Inclusion Criteria (Section 7.1 below).

The AEYE-DS device will be used in the study by clinicians who represent the actual end-users. These will be clinical personnel working in primary care facilities, who perform various screening activities for patients. The users will upload the de-identified study images and simulate the generation of a clinical decision based on the AEYE-DS algorithm results.

Evaluation of the study participant inclusion/exclusion criteria will be based on the review of clinical medical records and/or documented patient interviews conducted by the investigator or under the direction of the investigator in the application of the study inclusion and exclusion criteria, as summarized below.

To be enrolled in the study, patients must meet ALL of the inclusion criteria and NONE of the exclusion criteria designated below.

7.1 Inclusion Criteria:

1. Age ≥ 22
2. Male or female
3. Documented diagnosis of diabetes mellitus, meeting the criteria established by the American Diabetes Association (ADA) and World Health Organization (WHO):
 - a. Elevated Hemoglobin A1c (HbA1c) $\geq 6.5\%$ (48mmol/mol), based on repeated assessments, performed in a laboratory using a method that is NGSP certified and standardized to the DCCT assay **OR**
 - b. Fasting Plasma Glucose (FPG) ≥ 126 mg/dL (7.0 mmol/L), based on repeated assessments, where 'fasting' is defined as no caloric intake for at least 8 hours **OR**
 - c. Oral Glucose Tolerance Test (OGTT) with two hour plasma glucose (2-hr PG) ≥ 200 mg/dl (11.1 mmol/L), using the equivalent of an oral 75 g anhydrous glucose dose dissolved in water **OR**
 - d. Symptoms of hyperglycemia or hyperglycemic crisis with a random plasma glucose (RPG) ≥ 200 mg/dl (11.1 mmol/L)

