9.1 Screening

Investigators will screen participants based on the inclusion/exclusion criteria described above. Diabetic patients who require fundoscopy examination, meet the inclusion criteria and do not meet any clause of the exclusion criteria and volunteer to participate will join the study. A consent form will be signed by each patient. General patient demographics (including age, gender, race and ethnicity), diabetic history (including HbA1C, FPGL, etc.), ophthalmic history (including lens status, reported light sensitivity, as applicable), medical history, concomitant medications, fundoscopy system used, OCT system used, etc., will be obtained for each study case.

At the start of the study, all participants with diabetes who meet inclusion and exclusion criteria will be enrolled sequentially. To avoid excessive enrollment in any one stratum (no/mild DR or mtmDR), the totals will be monitored monthly and the study population will be enriched to ensure sufficient numbers of subjects with mtmDR. [REDACTED]

[REDACTED]

9.2 Data Acquisition (by Novice Operator):

The novice operator will obtain fundoscopy images from each eye of the patient, after the patient has signed an informed consent form. The novice operator is a staff personal from a primary care site, who has not previously performed ocular imaging. [REDACTED]

[REDACTED]

The novice operators will undergo a one-time standardized training program on how to acquire images, how to improve image quality if the AEYE-DS gives an insufficient quality output, and how to submit images for analysis to the AEYE-DS device. No additional training will be provided to the operators for the duration of the study.

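### PPV and NPV are planned from a sample to be enriched for mtmDR, and no visible text labels them as study-mix values or gives them at other prevalences (minor; redacted text may cover it)

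*Combined protocol and SAP*

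**What the plan says.** Section 11.9.5 first plans "A 2x2 table of the results of all subjects who had valid results on both AEYE-DS and the Reader Center", and then: "The positive and negative predictive values (PPV and NPV respectively) of the diagnosis together with their respective exact 95% confidence intervals will be presented". Section 8 also says that both predictive values will be determined, without qualification.

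On recruitment, section 9.1 begins: "At the start of the study, all participants with diabetes who meet inclusion and exclusion criteria will be enrolled sequentially". It then says that "the totals will be monitored monthly and the study population will be enriched to ensure sufficient numbers of subjects with mtmDR". The text directly after that is redacted.

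Later in 11.9.5 comes "Sensitivity and specificity, analyses will be carried out on the combined cohorts", again followed directly by redaction. That sentence names sensitivity and specificity but not PPV or NPV.

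The Sample Size row of the synopsis gives the minimum numbers: "At least 66 positive and 265 negative subjects are required to meet the primary and powered secondary endpoints".

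**The concern.** Sensitivity is computed among reference positives and specificity among reference negatives, so changing the ratio of the two groups does not change either by arithmetic. PPV mixes the groups. If enrichment lifts the share of mtmDR above that of the clinics where the device will be used, and sensitivity and specificity carry over, the study PPV overstates the clinic PPV and the study NPV slightly understates the clinic NPV. An exact binomial interval does not address this gap, because it describes sampling error around the study-mix value.

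The device is meant for screening in primary care, and section 8 describes the enrolled subjects as representing the target population. A reader could therefore take an unlabelled PPV as the chance that a positive result in a clinic is correct. What is at stake is the interpretation of a descriptive result, not the trial's decision.

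**Working it through.** **Inputs from the documents**
- Minimum counts: 66 positive, 265 negative (synopsis, Sample Size). Share positive: 66/(66 + 265) = 66/331 = 19.9%.
- Goals: exact one-sided 97.5% lower limits above 82% for sensitivity (Se) and 87% for specificity (Sp) (sections 11.4 and 11.9.2).
- The Se and Sp assumed for the sample size are not visible, so 66 and 265 can be neither confirmed nor refuted. They serve here only as a case mix.

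**Smallest passing counts (Clopper-Pearson lower limits)**
- Sensitivity: 61/66 gives 83.2%, 60/66 gives 81.3%. At least 61 are needed.
- Specificity: 242/265 gives 87.3%, 241/265 gives 86.8%. At least 242 are needed.

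**Assumed base case** (an illustration, not a forecast)
- 61/66 and 246/265 correct: Se = 0.9242, Sp = 0.9283, with 265 − 246 = 19 false positives and 66 − 61 = 5 false negatives.
- Direct PPV = 61/(61 + 19) = 61/80 = 76.3%, exact 95% interval 65.4 to 85.1%.
- Direct NPV = 246/(246 + 5) = 246/251 = 98.0%, exact 95% interval 95.4 to 99.4%.

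**The same Se and Sp at prevalence p**
- PPV = Se·p / [Se·p + (1 − Sp)(1 − p)]
- NPV = Sp(1 − p) / [Sp(1 − p) + (1 − Se)p]
- Variance of logit PPV at fixed p: (1 − Se)/(66·Se) + Sp/[265(1 − Sp)] = 0.0501
- Variance of logit NPV at fixed p: Se/[66(1 − Se)] + (1 − Sp)/(265·Sp) = 0.1851

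Example at p = 0.10: 0.0924/(0.0924 + 0.0645) = 58.9%.

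| Assumed prevalence | PPV (logit 95% CI) | NPV (logit 95% CI) |
|---|---|---|
| 20% | 76.3% (67.5 to 83.3) | 98.0% (95.5 to 99.1) |
| 15% | 69.5% (59.5 to 77.9) | 98.6% (96.8 to 99.4) |
| 10% | 58.9% (48.0 to 69.0) | 99.1% (97.9 to 99.6) |
| 5% | 40.4% (30.4 to 51.3) | 99.6% (99.0 to 99.8) |

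The PPV point value falls below the direct exact interval only when prevalence is under about 12.8%. NPV rises above its direct interval only under about 7.4%.

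**Other assumed accuracies**

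| Correct | Direct PPV (exact 95% CI) | PPV at 10% | Leaves the interval below |
|---|---|---|---|
| 61/66, 242/265 | 61/84 = 72.6% (61.8 to 81.8) | 54.2% | 13.2% |
| 61/66, 246/265 | 61/80 = 76.3% (65.4 to 85.1) | 58.9% | 12.8% |
| 63/66, 252/265 | 63/76 = 82.9% (72.5 to 90.6) | 68.4% | 11.9% |

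**Dependence on constant accuracy**

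With Se held, the clinic specificity at which clinic PPV equals the direct 76.25% is 1 − Se·p(1 − 0.7625)/[0.7625(1 − p)]. This is 94.9%, 96.8% and 98.5% at p = 15%, 10% and 5%, against 92.8% in the base case. At 10%, a specificity of 94.6% would bring PPV up to the direct lower limit of 65.4%.

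**What the documents say about prevalence**

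The only visible figures are worldwide: "over 35% have signs of DR, a third of them with vision threatening DR" (section 5, repeated in sections 1 and 12.2). Taken at face value that is 0.35/3 = 11.7% with vision-threatening disease, where the base-case PPV would be 63.0%. But these figures cover all people with diabetes and a different disease category, whereas section 7 requires: "The patients referred to the screening program must be without prior diagnoses of DR". They do not supply an mtmDR prevalence for the clinics.

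**The case against.** The strongest reply is redaction. Text is blacked out straight after the enrichment sentence in 9.1 and straight after the combined-cohorts sentence in 11.9.5, the two places where one would expect the handling of prevalence-dependent measures. The combined-cohorts sentence implies more than one cohort and leaves out PPV and NPV, so they may be handled separately, perhaps on the sequentially enrolled subjects only. This stands as a limit: the point can be put only against the visible text, and it lapses if the hidden text covers it.

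Second, the harm depends on facts not shown. The enrichment method is redacted, the realised mix need not be 19.9%, and clinic prevalence is unknown. At 15 to 20% the recomputed PPV stays inside the direct interval. Even at 10%, the two intervals (48.0 to 69.0% and 65.4 to 85.1%) overlap. This also stands, and is why the size is given as a range.

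Third, PPV and NPV are not among the visible endpoints in 11.2, carry no hypothesis in 11.3 and play no part in the success rule. The direct estimates are correct for the sample analysed, and the planned 2x2 table lets a careful reader recompute them. This keeps the point minor. It does not remove it: a grid fixed in advance avoids choosing prevalences after the results are known and spares readers the calculation.

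**Conclusion.** The point holds as a minor, optional improvement to reporting. On the visible text, the plan presents PPV and NPV with exact intervals from a sample whose case mix is partly set by design, without marking them as study-mix values. In the base case PPV falls from 76.3% to 58.9% at 10% prevalence, about 17 points, and to 40.4% at 5%. Across the three assumed accuracies the fall at 10% is 14.5 to 18.4 points (82.9 − 68.4 and 72.6 − 54.2). NPV moves by less than 2 points.

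This rests on three assumptions: the minimum counts as the study mix, clinic prevalence below that mix, and sensitivity and specificity that carry over to the clinic. None can be checked from the documents. Sensitivity, specificity and the success decision are not affected.

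**What to change.** In 11.9.5, unless the redacted text already does this:

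1. Label the direct PPV and NPV as specific to the study sample and its case mix.
2. Add Bayes-rule PPV and NPV from the study sensitivity and specificity, with logit (delta-method) 95% intervals, over a prevalence grid stated in advance, for example 5, 10, 15 and 20%. State the assumption that sensitivity and specificity carry over.
3. If the subjects enrolled sequentially before enrichment can already be identified, also show the values at their observed mtmDR prevalence.

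The cost is one line of wording and one short table from estimates already planned. The label and grid need no new data. The added PPV may look less favourable than the direct one. The success rule stays as it is.

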11.9.6 Analysis of Secondary Endpoints

The powered secondary efficacy analysis will present the estimation of sensitivity and specificity of the AEYE-DS device to detect mtmDR on digital funduscopy images (acquired by the TopCon NW400 funduscopy device based on 2 images obtained per eye, one macula centered and one optic disc centered) together with the lower limit of their respective one-sided exact 97.5% confidence intervals. [REDACTED]

[REDACTED]

[REDACTED]

[REDACTED]

[REDACTED]

[REDACTED]

11.9.7 Safety Assessments and Adverse Events

[REDACTED]

11.9.8 Poolability

[REDACTED]

11.9.9 Handling of Missing Data

Subjects with missing data will be compared to those with complete data, with respect to demographic and perhaps other baseline characteristics.

As a sensitivity analysis, the primary and powered secondary endpoints will be analyzed considering a non-analyzable result of the AEYE-DS as “negative” for the calculation of sensitivity, and “positive” for the calculation of specificity.

12 RISK / BENEFIT ANALYSIS

12.1 Risks

The risks to patients resulting from potential device hazards have been analyzed using the Risk Management Standard - ISO 14971. The different types of hazards were identified and evaluated using risk assessment numerical parameters. Applicable controls for the risks were analyzed. [REDACTED]

[REDACTED]

[REDACTED]

[REDACTED]

[REDACTED]

[REDACTED]

[REDACTED]

12.2 Benefits

Diabetic Retinopathy (DR) is the leading cause of vision loss in adults between ages 20-74 [Cheung et al., 2010], and ranked as one of the most common causes of preventable blindness [Bourne, 2013]. Based on a recent global report [WHO, 2014], there are over 422 million people worldwide with diabetes, and over 35% have signs of DR, a third of them with vision threatening DR. With the prevalence of diabetes expected to increase 50% over the next 10 years, screening rates, detection, and treatment must be addressed in order to prevent a significant increase in unnecessary blindness across the United States.

Early detection of retinopathy is an important part of managing care for people with diabetes, yet many patients with diabetes are not adequately screened for diabetic retinopathy. A 1990 program launched by the American Academy of Ophthalmology (AAO), known as Diabetes 2000, was designed to increase nationwide DR screening rates. However, after 20 years of implementation, screening rates continue to stagnate, with only 50-60% of diabetic patients properly evaluated.

A DR screening solution at the point of primary care is expected to help address the unmet need, lack of access, and racial and ethnic disparity issues that have persisted for decades. An automated screening device would allow for immediate screening results at the point of care and standardization of results. Ophthalmic key opinion leaders state that an automated diabetic retinopathy screening device in the hands of primary care healthcare providers would increase screening rates and detect more treatable vision threatening DR.

The current proposed study will validate the sensitivity and specificity of the AEYE-DS output by a novice operator compared to the diagnostic determination by an independent, blinded panel of expert ophthalmologist at the reading center.

13 ETHICAL ASPECTS

13.1 Study-Specific Design Considerations

Subjects/cases will be carefully screened using the study eligibility criteria prior to enrollment in the study.

13.2 Regulatory Ethics Compliance

13.2.1 Investigators Responsibilities

The investigator is responsible for ensuring that the clinical study is performed in accordance with the protocol, current ICH guidelines on Good Clinical Practice (GCP), and applicable regulatory requirements.

GCP is an international ethical and scientific quality standard for designing, conducting, recording, and reporting studies that involve the participation of human subjects. Compliance with this standard provides public assurance that the rights, safety, and well-being of study subjects are protected, consistent with the principles that originated in the Declaration of Helsinki, and that the clinical study data are credible.

13.2.2 Independent Ethics Committee or Institutional Review Board

Before the start of the study, the investigator will provide the IEC/IRB with current and complete copies of the following documents:

- Final protocol and if applicable, amendments
- Informed consent form
- Investigator's Brochure (or equivalent information) and amendments
- Investigator's curriculum vitae or equivalent information (unless not required, as documented by IEC/IRB)
- Information regarding funding, name of the sponsor, institutional affiliations, and other potential conflicts of interest
- Any other documents that the IEC/IRB requests to fulfill its obligation

This study will be undertaken only after IEC/IRB has given full approval of the final protocol, amendments (if any), and informed consent and after the sponsor has received a copy of this approval. This approval letter must be dated and must clearly identify the documents being approved.

During the study the investigator will send the following documents to the IEC/IRB for their review and approval, where appropriate:

- Protocol amendments
- Investigator's Brochure amendments or new edition(s)
- Summaries of the status of the study (at least annually or at intervals stipulated in guidelines of the IEC/IRB)

- Reports of any serious adverse events, if applicable
- Deviations from or changes to the protocol
- Notification if new investigator is responsible for the study at the site
- Any other requirements of the IEC/IRB

At least once a year the IEC/IRB will be asked to review and re-approve this clinical study. This request and approval should be documented in writing.

At the end of the study, the investigator (or sponsor where required) will notify the IEC/IRB about the study completion.

13.2.3 Informed Consent

Each subject must give written consent according to local requirements after the nature of the study has been fully explained. The consent form must be signed before performance of any study-related activity. The consent form used must be approved by both the sponsor and by the reviewing IEC/IRB. The informed consent should be in accordance with principles set forth in the Declaration of Helsinki, current ICH and GCP guidelines, applicable regulatory requirements, and sponsor policy.

Before entry into the study, the investigator or an authorized member of the investigational staff must explain to potential subjects the aims, methods, reasonably anticipated benefits, and potential hazards of the study, and any discomfort it may entail. Subjects will be informed that their participation is voluntary and that they may withdraw consent to participate at any time. They will be informed that choosing not to participate will not affect the care the subject will receive for the treatment for his/her disease. Subjects will be told that alternative treatments are available if they refuse to take part and that such refusal will not prejudice future treatment. Finally they will be told that their records may be accessed by health authorities without violating the confidentiality of the subject, to the extent permitted by the applicable law(s) or regulations. By signing the informed consent form the subject is authorizing such access.

The subject will be given sufficient time to read the informed consent form and the opportunity to ask questions. After this explanation and before entry into the study, consent should be appropriately recorded by name of the subject, subject's signature and date of signature. After having obtained the consent, a copy of the informed consent form must be given to the subject. If the subject or legally acceptable representative is unable to read or write, an impartial witness should be present for the entire informed consent process (which includes reading and explaining all written explanations) and should personally date and sign the informed consent form after the oral consent of the subject or legally acceptable representative is obtained.

